GCS Co., Ltd.	GANA X® CIP #21E0805	Final version 3.0 Date: 07/04/2022	Page 1/5
---------------	-------------------------	---------------------------------------	----------

SUMMARY OF THE CLINICAL INVESTIGATION PLAN # 21E0805

ANSM registration #:	2021-A02728-33
Clinical investigation plan #:	21E0805
Title of the clinical investigation:	CLINICAL STUDY FOR THE EFFECTIVENESS OF USE OF AN INJECTABLE MEDICAL DEVICE GANA X® IN THE TREATMENT OF BUTTOCKS VOLUME DEPRESSION
Sponsor:	GCS Co., Ltd. [name]
Development phase	Post market study Interventional Device used according to Instruction For Use (IFU)
Objectives:	
The primary objective is to evaluate the effectiveness of Gana X® in improving buttocks volume 6 months after treatment.
 
The secondary objectives of the study are:
 
 - to evaluate the effectiveness of Gana X® in improving buttocks volume 1½, 9, 12, 18 and 24 months after treatment. - to evaluate the effectiveness of Gana X® on the global aesthetic improvement of buttocks 1½, 6, 9, 12, 18, 24 months after treatment as rated by the evaluator. - to evaluate the effectiveness of Gana X® on the global aesthetic improvement of buttocks 1½, 6, 9, 12, 18, 24 months after treatment as rated by the subjects. - To evaluate the subject satisfaction with Gana X® 1½, 6, 9, 12, 18 and 24 months after treatment. - To evaluate the injector satisfaction with Gana X® after initial and touch-up injection if applicable. - To evaluate the safety of Gana X®.
Design:	The study will be: 
 • In open, • Single center.
Planned Sample Size:	55 subjects included.
Number of investigational study sites:	1 site (France).
Inclusion criteria:	
 1. Healthy Subject. 2. Sex: male or female. 3. Age: between 18 and 65 years. 4. Subject with mild to moderate buttock volume depression and/or seeking buttocks volume augmentation based on investigator evaluation. 5. Subject willing to abstain from other body contouring procedures during the whole study period. 6. Subject psychologically able to understand the study related information and to give a written informed consent. 7. Subject having given freely and expressly his/her informed consent. 8. Subject willing to have photographs taken.

GCS Co., Ltd.	GANA X® CIP #21E0805	Final version 3.0 Date: 07/04/2022	Page 2/5
---------------	-------------------------	---------------------------------------	----------

	
9. Subject affiliated to a health social security system.
 
10. Female of childbearing potential should use a contraceptive regimen recognized as effective since at least 12 weeks before screening visit and during the whole study period.

Exclusion criteria:	
1. Pregnant or nursing woman or having given birth within the last year or planning a pregnancy during the study.
 
2. Excessive subcutaneous fat in the area to be treated.
 
3. Excessive skin laxity on the area to be treated.
 
4. Severe buttocks ptosis.
 
5. Subject who had been deprived of their freedom by administrative or legal decision or who is under guardianship.
 
6. Subject in a social or sanitary establishment
 
7. Subject participation to another research on human beings or who is in an exclusion period of one.
 
8. Subject having already received 4500 euros indemnities for participation in research involving human beings in the 12 previous months or exceeding these 4500 euros with his participation in the present study.
 
9. Subject suspected to be non-compliant according to the investigator's judgment.
 
10. Subject suffering from a severe or progressive disease or any other pathology that may interfere with the evaluation of the study results.
 
11. Subject with known history of or suffering from autoimmune disease and/or immune deficiency.
 
12. Subject with a history of cellulitis, streptococcal disease, such as acute rheumatic fever or recurrent sore throats and in case of acute rheumatic fever with heart complications.
 
13. Subject suffering from inflammatory and/or infectious cutaneous disorders in or near the studied zones (e.g. acne, chronic eczema, atopic dermatitis...).
 
14. Subject with an abscess, unhealed wound, or a cancerous or precancerous lesion on the studied zone.
 
15. Subject prone to develop inflammatory skin conditions or having tendency to bleeding disorders.
 
16. Subject with a tendency to develop keloids or hypertrophic scarring.
 
17. Subject with significant scarring, open wounds, lesions or tattoos in or near the area to be treated.
 
18. Subject having history of allergy or anaphylactic shock including hypersensitivity to Poly-l-lactic acid, to lidocaine or to one of the components of the tested devices or antiseptic solution.
 
19. Subject having received a dose of COVID-19 vaccine within the 14 days prior to injection visits or planning to receive a dose in the 14 days following injections.
 
20. Subject having received treatment on or near the buttocks (laser, dermabrasion, surgery, radiofrequency, cryolipolysis, buttocks electrostimulation, endermologie, liposuction, other energy-based treatment, surgery...) within the 12 months prior to screening visit.
 
21. Subject having received injection with a resorbable filling product in or near the buttocks within the 12 months prior to screening visit.
 
22. Subject having received at any time the following treatments in the area to be treated:
 
 • Buttocks implants;

GCS Co., Ltd.	GANA X® CIP #21E0805	Final version 3.0 Date: 07/04/2022	Page 3/5
---------------	-------------------------	---------------------------------------	----------

	
 • Buttocks fillers (e.g., silicone, semi-permanent or permanent fillers or autologous fat injections); • Injections for the treatment of cellulitis. 
23. Subject having started or changed her oral contraceptive or any other hormonal treatment during 12 weeks prior to screening visit.
 
24. Subject using medication such as aspirin, nonsteroidal anti-inflammatory drugs (NSAID) (ibuprofen, naproxen, ...), antiplatelet agents, anticoagulants or other substances known to prolong bleeding time within 1 week prior to injection visits.
 
25. Subject undergoing a topical treatment on the test area or a systemic treatment:
 
 • Antihistamines during the 2 weeks prior to injections visits (D0 and touch-up visit). • Immunosuppressors and/or corticoids during the 4 weeks prior to injections visits (D0 and touch-up visit). • Retinoids during the 6 months prior to injections visits (D0 and touch-up visit). 
26. Intensive exposure to sunlight or UV-rays within the month before injection visits and one month after.
 
27. Subject planning to loss or gain weight for the duration of the study.
 
28. Subject planning to change her/his life habits during the study.

Investigational device: Name / code Classification Ingredient Galenic form Administration route	Gana X® Class III medical device Poly-L-Lactic Acid (630mg), Sodium Carboxymethyl Cellulose, Mannitol. Sterile freeze-dried preparation (powder) Injection in the deep dermis and subcutaneous layer.
Endpoints:	
Primary effectiveness endpoint: Mean change in buttocks volume from baseline to 6 months after treatment using fringe projection system.
 
Secondary effectiveness endpoints:
 
 - Mean change in buttocks volume from baseline to 1^{1/2}, 9, 12, 18 and 24 months after treatment using fringe projection system. - GAIS responder rates 1^{1/2}, 6, 9, 12, 18 and 24 months after treatment as assessed by an independent live evaluator. A responder is defined as a subject having "Improved", "Much improved" or "Very much improved" score according to GAIS. - GAIS responder rates 1^{1/2}, 6, 9, 12, 18 and 24 months after treatment as assessed by the subjects. - Proportion of satisfied subjects 1^{1/2}, 6, 9, 12, 18 and 24 months after treatment using a questionnaire. - Injector's satisfaction regarding injection quality after initial and touch-up injection using a questionnaire. 
Secondary safety endpoints: Investigational device safety will be assessed by collection of Injection Site Reactions (ISRs) and Adverse Events (AEs) throughout

GCS Co., Ltd.	GANA X® CIP #21E0805	Final version 3.0 Date: 07/04/2022	Page 4/5
---------------	-------------------------	---------------------------------------	----------

	
the study by the investigator. Subjects will record ISRs and AEs in their subject diaries.

Study Procedures:	
A screening visit will allow to inform and preselect the subjects.
 
On D0, fringe projection acquisitions and photographs will be done before injection. Eligible subjects will receive a first injection of the investigational device. Immediately after injection, injector's treatment satisfaction will be collected. Investigator evaluator will collect AEs and ISRs immediately after injection.
 
A month and a half after initial injection (M1^{1/2}), GAIS scoring, fringe projection acquisitions and photographs will be done before touch-up injection (if applicable). A touch-up injection will be made if necessary, according to injector and subject opinion. Investigator evaluator will collect AEs and ISRs before and after touch-up if applicable. Subject's treatment satisfaction and injector's treatment satisfaction (if applicable) will be collected.
 
Six (M6), nine (M9), twelve (M12), eighteen (M18) and twenty-four (M24) months after initial injection, effectiveness scoring (GAIS scale), fringe projection acquisitions and photographs will be done. Subject's treatment satisfaction will be collected. Investigator evaluator will collect AEs and ISRs

Statistical methods:	
For the primary evaluation criterion:
 
The primary endpoint is the mean change in buttocks volume from baseline to 6 months after treatment using fringe projection system. Descriptive statistics for quantitative data (N, mean, standard deviation, minimum and maximum) will be presented at D0 before injection and M6.
 
Inferential analysis:
 
A Wilcoxon signed rank test, or a paired t test will be applied to evaluate the change from baseline (D0 before injection) to M6. The normality assumption will be tested using a Shapiro Wilk test ($\alpha=0.01$). The bilateral approach will be used.
 
For the secondary evaluation criteria:
 
All the variables will be described using adapted statistics according to their type (quantitative data or qualitative data). For quantitative data a Wilcoxon or paired t test will be applied to assess the change from baseline.
 
The bilateral approach will be used with a significance level of 0.05.

Foreseen study duration:	
Clinical investigation beginning: Q1 2022
 
Clinical investigation end: Q3 2024
 
Inclusion duration: Maximum 6 months
 
Clinical investigation global duration: 30 months
 
Duration by subject: 24 months + screening period

FLOW-CHART

Procedure	Visit 1 Screening	Visit 2 Day 0	Visit 3 M1 ^{1/2}	Visit 4 M6	Visit 5 M9	Visit 6 M12	Visit 7 M18	Visit 8 M24
Days	D-X	D0	D40 ± 2	D160 ± 4	D270 ± 4	D365 ± 7	D540 ± 14	D730 ± 14
Informed consent form signature	●							
Medical examination	●							
Medical history and previous and concomitant treatments collection	●							
Checking of the inclusion and exclusion criteria	●							
Pregnancy test		● ^b	● ^b					
Confirmation of eligibility		● ^b						
Photographs		● ^b	● ^b	●	●	●	●	●
Fringe projection acquisitions (2 areas)		● ^b	● ^b	●	●	●	●	●
Injection + anaesthesia (if necessary)		●	● Touch up					
GAIS live assessment by an independent evaluator			● ^b	●	●	●	●	●
GAIS assessment by the subjects			● ^b	●	●	●	●	●
Subjective evaluation questionnaire for subjects			● ^b	●	●	●	●	●
ISR live assessment by an independent evaluator		● ^a	● ^{b+a}	●	●	●	●	●
ISR assessment by the subjects		Completed each day during 4 weeks after injection at home by the subject.						
Subjective evaluation questionnaire for injector		● ^a	● ^a					
AE and concomitant treatments and procedures collection	●	●	●	●	●	●	●	●
Study end								●

Keys: ^b: Before injection; ^a: After injection

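### Does the and/or in inclusion criterion 4 admit a population wider than the titled volume depression, so that the plan needs a depression grade and a subset result?

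*Combined protocol and SAP*

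**What the plan says.** Inclusion criterion 4 requires a "Subject with mild to moderate buttock volume depression and/or seeking buttocks volume augmentation based on investigator evaluation". The title of the investigation describes the device's use "IN THE TREATMENT OF BUTTOCKS VOLUME DEPRESSION", with no grade attached.

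Under Objectives, the primary aim is effectiveness "in improving buttocks volume 6 months after treatment". Under Endpoints, the primary measure is "Mean change in buttocks volume from baseline to 6 months after treatment using fringe projection system". Neither mentions depression.

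Exclusion criteria 2 to 4 deal with excess fat, skin laxity and ptosis. The last of these ("Severe buttocks ptosis") is the nearest thing to a severity limit, and it does not concern volume depression.

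The Flow-chart lists "Checking of the inclusion and exclusion criteria" at Visit 1 but has no row for a depression grade. Under Study Procedures, "On D0, fringe projection acquisitions and photographs will be done before injection". Statistical methods names a paired t test or a Wilcoxon signed rank test for the D0-to-M6 change, and no subgroup.

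**The concern.** The words and/or make each half of criterion 4 sufficient by itself, and the severity wording belongs to the first half only. A subject who seeks augmentation can therefore qualify with no depression at all. The closing reference to the investigator's evaluation adds judgement but no threshold, and no exclusion supplies one. The summary thus puts no floor on how many of the 55 subjects have the condition in the title.

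What would be at stake is interpretation. If many subjects had no depression and responded differently, the all-subject mean change could not be read as the effect in volume depression. From what is planned here, a reader could not tell how many subjects had that condition or how they did. The GAIS responder and satisfaction rates are pooled in the same way. In a single-arm open study, the baseline description is the main guide to whom the result applies.

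**Working it through.** **1. Which entrants fall outside the title?** The title names depression without a grade. Mild to moderate appears only in criterion 4. A subject with severe depression is therefore inside the titled condition, and only a subject with no depression is outside it. A mild-to-moderate subset would not answer the question the title raises. The relevant split is depression of any grade against none.

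**2. Does the planned analysis match the people enrolled?**

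| Element | Refers to |
|---|---|
| Title | volume depression |
| Criterion 4 | depression, or wish for augmentation, or both |
| Primary objective | buttocks volume at 6 months |
| Primary endpoint | mean volume change, D0 to M6 |
| Primary test | within-subject change from D0 |

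Only the title is narrower than criterion 4. Volume can be measured in every entrant whether or not depression is present, and each subject's own pre-injection value is the reference. Depression status enters neither the estimate nor the test.

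**3. How far could the all-subject mean lie from the mean in subjects with depression?** Let *p* be the share of subjects with depression and *d* the mean change in those without minus the mean change in those with. Then

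all-subject mean − mean in subjects with depression = (1 − *p*) × *d*.

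The documents give neither *p* nor *d*, so both are assumed here. *d* is in units of the within-group SD of change, taken as common to both groups.

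| *p* | *d* = 0 | *d* = 0.25 SD | *d* = 0.5 SD |
|---|---|---|---|
| 100% | 0 | 0 | 0 |
| 75% | 0 | 0.06 | 0.13 |
| 50% | 0 | 0.13 | 0.25 |
| 25% | 0 | 0.19 | 0.38 |

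These are illustrations and not bounds: *p* = 10% with *d* = 0.5 gives 0.90 × 0.5 = 0.45 SD. The sign could go either way.

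**4. What would a subset result add?** The 95% half-width of a mean, in SD units, is t(0.975, n−1)/√n, assuming every included subject has an M6 value.

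- n = 55: 0.27
- n = 41 (about 75%): 0.32
- n = 28 (about 50%): 0.39
- n = 14 (about 25%): 0.58

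For the difference between subset and rest, the half-width is t(0.975, 53) × √(1/n₁ + 1/n₂).

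- 28 against 27: 0.54
- 41 against 14, or 14 against 41: 0.62

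Even the larger assumed difference, 0.5 SD, is smaller than the half-width of its own estimate in every split shown. The subset row could describe, but it could not settle whether response depends on depression status.

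**The case for a change.** The best argument for a change is that the remedy is cheap. One field at the existing screening check, and one line in the baseline table, would tell a reader how many of the 55 had the titled condition. The 0.5 SD scenario is not negligible where few subjects have depression. The GAIS, which starts at M1½ and rates improvement, cannot supply entry status. D0 fringe projection measures volume, but no threshold turns it into a grade.

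The literal reading of criterion 4 stands, and so does the absence of a grade from the summary. A count of subjects with depression would be a useful descriptive line. Three things keep this from being a needed change.

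- The count alters no planned estimate, test or sample size.
- Only a five-page summary is visible. The full plan, the case report form and the instructions for use, which the summary says govern use of the device, may already limit or record depression status. Their content is unknown, so this is a caution against calling the item missing, and no proof that it exists.
- Version 3.0 is dated 07/04/2022, the planned start was Q1 2022 and inclusion lasts at most 6 months. On those dates some subjects may already have been enrolled. Completing the field for them could need someone to grade the D0 photographs, which costs more than a form field and mixes live with photographic grades.

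**Conclusion.** No change to the plan follows. Criterion 4 can admit subjects without depression and the title does not say so, but this is a labelling mismatch. Broad entry is a legitimate choice in a post-market, open, single-centre study. The primary objective, endpoint and within-subject test fit the population that criterion 4 defines, so following the plan as written gives a sound answer to its stated question.

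What would not be supported is calling the all-subject mean the effect in volume depression for subjects who have none. An analyst avoids that by describing the enrolled population in the words of criterion 4. The size of any discrepancy cannot be established from the documents. It is zero if every subject has depression or if response does not differ by status, and 0.06 to 0.38 SD over the non-zero mixes and differences assumed above, with larger values possible outside them. The conclusion does not depend on those figures. It rests on the objective being about volume in the enrolled subjects, and it would change only if the sponsor made a formal claim confined to volume depression.

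### The primary endpoint is set at 6 months, but the flow-chart schedules the M6 visit at D160 ± 4, a window that does not contain 6 months

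*Combined protocol and SAP*

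**What the plan says.** The primary objective concerns the effectiveness of the device "in improving buttocks volume 6 months after treatment", and the primary effectiveness endpoint is "Mean change in buttocks volume from baseline to 6 months after treatment using fringe projection system". The Study Procedures section fixes the starting point of the clock: the later visits take place "Six (M6), nine (M9), twelve (M12), eighteen (M18) and twenty-four (M24) months after initial injection". Under Statistical methods, the primary inferential analysis reads "A Wilcoxon signed rank test, or a paired t test will be applied to evaluate the change from baseline (D0 before injection) to M6".

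The Days row of the flow-chart gives Visits 3 to 8 (M1½, M6, M9, M12, M18, M24) as "D40 ± 2 D160 ± 4 D270 ± 4 D365 ± 7 D540 ± 14 D730 ± 14". Visit 4, labelled M6, is the second entry: D160 with a tolerance of 4 days.

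Three secondary endpoints at the same visit also carry the 6-month label: the evaluator's GAIS responder rate ("6, 9, 12, 18 and 24 months after treatment as assessed by an independent live evaluator"), the subject's GAIS responder rate, and the proportion of satisfied subjects.

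**The concern.** D160 is too early for a 6-month visit under any usual reading of a month, and nothing in the document explains it or defines a month differently. One visit cannot be both six months after the initial injection and inside the scheduled window. A site that follows the flow-chart produces a Day-160 measurement that will be reported as the 6-month result. A site that schedules a true 6-month visit records a window deviation for every subject at the primary assessment.

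What is at stake is the time point that the primary result is said to describe. In a single-arm study whose claim is a change from baseline at a stated time, that time is part of what is being estimated. The validity of the test is not at stake: a paired t or signed-rank test works on within-subject differences from independent subjects, whichever day the second measurement is taken.

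**Working it through.** **Inputs.** Visit labels, days and tolerances come from the flow-chart, and the starting point (the initial injection, D0) from Study Procedures. The document does not define a month, so I tried 28 days, 30 days, the mean calendar month (365.25/12 = 30.44 days) and exact calendar dates.

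**The M6 window in months.** The window is 160 − 4 = D156 to 160 + 4 = D164. In mean calendar months, 156/30.44 = 5.13, 160/30.44 = 5.26 and 164/30.44 = 5.39.

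**Six months in days.**

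| Month convention | 6 months | Gap from D160 | Gap from D164 |
|---|---|---|---|
| 28 days | D168 | 8 | 4 |
| 30 days | D180 | 20 (20/180 = 11%) | 16 |
| 30.44 days | D182.6 | 22.6 (22.6/182.6 = 12%) | 18.6 |
| Exact dates, every D0 in 2022 | D181 to D184 | 21 to 24 | 17 to 20 |

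No convention puts 6 months inside D156 to D164. On exact dates, 0 of 365 possible D0 dates do so.

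**Month length each window would need.** Divide the two ends of the window by the nominal number of months.

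| Visit | Window | Days per month needed | Contains nominal month at 30 / 30.44 days | Exact dates, D0 in 2022 |
|---|---|---|---|---|
| M1½ | D38–D42 | 38/1.5 to 42/1.5 = 25.3–28.0 | no / no | not computed |
| M6 | D156–D164 | 156/6 to 164/6 = 26.0–27.3 | no / no | 0 of 365 |
| M9 | D266–D274 | 266/9 to 274/9 = 29.56–30.44 | yes / yes | 275 of 365 |
| M12 | D358–D372 | 358/12 to 372/12 = 29.83–31.0 | yes / yes | 365 of 365 |
| M18 | D526–D554 | 526/18 to 554/18 = 29.2–30.8 | yes / yes | 365 of 365 |
| M24 | D716–D744 | 716/24 to 744/24 = 29.83–31.0 | yes / yes | 365 of 365 |

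The M9 to M24 windows jointly need a month of 29.83 to 30.44 days. M6 needs 26.0 to 27.3 days. The two ranges do not overlap, so no single month length fits M6 and the later visits.

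**A different starting point.** The objective and endpoint say only that the time runs from treatment. If it ran from the touch-up visit, the interval would be 160 − 40 = 120 days (156 − 42 = 114 to 164 − 38 = 126), about 4 months, which widens the gap.

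**The case against.** The strongest case on the other side concerns size and framing, since the arithmetic is not in dispute.

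- **The analysed visit is identifiable.** The flow-chart labels Visit 4 as M6 with one explicit day, and the test compares D0 with M6. A site can apply the Days row without ambiguity. This stands, but the visit then does not meet the 6-month definition in the objective, the endpoint and the procedures.
- **The impact is a label about three weeks off.** The test stays valid, and the document gives no time course for volume, so no bias can be sized. This stands and limits the severity. It does not make the endpoint correctly described.
- **D160 may be deliberate.** M1½ and M6 have the same ratio, 40/1.5 = 160/6 = 26.67 days per month, so the early visits may share a basis and D160 need not be a slip. For this reason I do not say which time is intended. The shared ratio still does not make D160 six months.
- **M9 is not perfectly clean.** On mean calendar months it falls on D273.94 against an upper limit of D274, and on exact dates 90 of 365 start dates (25%) miss the window, by at most 276 − 274 = 2 days. The M6 shortfall is 17 to 20 days on the same count.
- **The source is limited.** The document is a summary of the clinical investigation plan, so a fuller text could explain D160, and a misread table cell cannot be excluded. Nothing in the available text points to either.

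**Conclusion.** The concern holds. The plan sets its sole primary endpoint at 6 months from the initial injection and schedules the measurement at D156 to D164, or 5.13 to 5.39 mean calendar months. The target day is 20 to 23 days early on 30-day or mean calendar months, about five times the 4-day tolerance. Four endpoints are affected at this visit: one primary and three secondary. M1½ shows a smaller mismatch of the same kind: 1.5 months is D45 to D46 against D38 to D42, although 28-day months (D42) would just fit there.

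This rests on the flow-chart being transcribed correctly and on the summary reflecting the full plan. The document does not show which timing is intended, and the size and direction of any effect on the volume result cannot be derived from it. The point should be fixed. It does not invalidate the analysis.

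**What to change.** Check D160 against the full plan, then reconcile the passages in one of two ways:

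1. If 6 months is intended, give the Visit 4 assessment a target day and window that contain 6 months from the initial injection.
2. If D160 is intended, or those visits have already taken place, restate the primary objective, the primary endpoint and the other M6 endpoints as Day 160 after the initial injection, and report them that way.

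Two minor edits belong in the same change. State in the objectives and endpoints that time runs from the initial injection, as Study Procedures does. Also reconcile the M1½ label with D40 ± 2; I propose no day for it, because the touch-up is given at that visit.

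The cost is a correction to the flow-chart or to the endpoint wording. If the assessment moves, it moves by about three weeks within the existing 24-month follow-up, with no added visit, staff or subject. Because the plan is a final version 3.0 with a start foreseen in Q1 2022, the change would need an amendment, and the study may already be running.

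### M9 to M24 volume change: the only stated inference is a paired test against baseline, which is biased if dropout depends on response; a repeated-measures model would use leavers' earlier volumes

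*Combined protocol and SAP*

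**What the plan says.** The Objectives row makes durability a secondary aim: "to evaluate the effectiveness of Gana X® in improving buttocks volume 1½, 9, 12, 18 and 24 months after treatment". The Endpoints row turns this into mean change from baseline at 1½ months and at "9, 12, 18 and 24 months after treatment using fringe projection system". The Flow-chart schedules fringe projection acquisition of two areas at D0, M1½, M6, M9, M12, M18 and M24.

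Under Statistical methods, the primary M6 analysis is: "A Wilcoxon signed rank test, or a paired t test will be applied to evaluate the change from baseline (D0 before injection) to M6". For secondary criteria the summary gives descriptive statistics by variable type and then "For quantitative data a Wilcoxon or paired t test will be applied to assess the change from baseline", two-sided at 0.05. The sample size row reads "55 subjects included". The design is open and single-centre, and no control arm is described. The summary states no repeated-measures model, imputation rule, analysis set or expected dropout.

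**The concern.** A paired test needs two values from the same subject. Someone measured at D0, M1½, M6 and M9 who then leaves adds nothing to the M12, M18 or M24 estimates, even though the earlier volumes carry information about the missing ones. With one group, the late means carry the whole message about how long the effect lasts. If those who leave differ in volume change from those who stay, the late means describe the stayers only, and the error builds up over the visits at which durability is judged.

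**Working it through.** **The plan's own figure.** There is none to reproduce: the 55 comes without an effect size, SD, power or dropout rate.

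**Inputs from the documents.** 55 subjects, one group, six post-baseline volume visits, a paired test at each visit.

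**Assumed inputs.**
- SD of change 1 at every visit; all results are in SDs of the change.
- Mean changes 0.4, 0.8, 0.7, 0.6, 0.5 and 0.4 at M1½, M6, M9, M12, M18 and M24.
- Correlation between visits AR(1) 0.7, AR(1) 0.8, exchangeable 0.5 or exchangeable 0.7. Ranges below run over these four.
- Permanent dropout before M9, M12, M18 or M24. The log-odds of leaving rise by 0.5 (weak link), 1 (strong) or 1.5 (steeper) per SD of lower last observed change. The intercept is set to give 10%, 20% or 30% missing at M24.
- 2,500 simulated trials per cell, Monte Carlo error about 0.003.

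**Step 1, where the bias comes from.** Let p be the share missing, A the mean of attenders and L the mean that leavers would have had. The full mean is (1 − p)A + pL, so

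bias = A − [(1 − p)A + pL] = p(A − L).

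At p = 0.20, a bias of 0.09-0.14 means a gap A − L of 0.09/0.20 = 0.45 to 0.14/0.20 = 0.70 SD.

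**Step 2, attenders at M24 (true change 0.40, normal data).** At 20% loss and slope 1 the attender means, in the order of correlations above, were 0.490, 0.513, 0.497 and 0.534, so the bias is 0.090, 0.113, 0.097 and 0.134. A single sample of 60,000 gave 0.103-0.140, hence the rounded 0.09-0.14.

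| Loss at M24 | slope 0.5 | slope 1 | slope 1.5 |
|---|---|---|---|
| 10% | 0.02-0.04 | 0.04-0.07 | 0.06-0.09 |
| 20% | 0.05-0.08 | 0.09-0.14 | 0.11-0.18 |
| 30% | 0.07-0.12 | 0.13-0.21 | 0.17-0.26 |

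For scale, 20% loss leaves 44 subjects, and 1/√44 = 0.15. At slope 1 the bias is therefore below one standard error at 20% loss. At 30% loss (38.5 subjects on average, 1/√38.5 = 0.16) it can exceed one.

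At 20% loss and slope 1 the bias grows by visit: 0.03-0.04 (M9), 0.05-0.07 (M12), 0.08-0.10 (M18), 0.09-0.14 (M24).

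**Step 3, consequences at slope 1.** Paired 95% interval coverage is 92-94%, 86-90% and 75-87% at 10%, 20% and 30% loss. A separate run with a true M24 change of zero and exchangeable correlation 0.7 had the nominal 5% paired t test reject in 7%, 15% and 26% of trials.

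**Step 4, the likelihood model on the same data.** At 20% loss the M24 estimate was 0.396-0.405, within 0.01 of the truth. Root mean squared error at slope 1 was 0.142-0.153, against 0.175-0.197 for attenders.

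**Step 5, other conditions at 20% loss.**
- Dropout unrelated to response: no bias either way; standard error 0.15-0.16 (attenders) and 0.14-0.15 (model).
- Better responders leave: attenders 0.09-0.14 too low.
- Right-skewed changes, slope 1: attender bias 0.05-0.10, coverage 94-96%; model up to about 0.02 too high.
- Dropout driven by the unseen current value, slope 1: attenders +0.12 to +0.15; model still +0.03 to +0.07. By Step 1 that residual equals a shift in leavers of 0.030/0.20 = 0.15 to 0.063/0.20 = 0.32 SD.

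**Step 6, can the data reveal the problem?** At slope 1 with normal data, leavers' M6 change is 0.60-0.77 SD below stayers'. A two-sample t test finds this in 27-41%, 44-64% and 58-77% of trials at 10%, 20% and 30% loss, and in 13-29% with skewed data at 20% loss. The comparison is informative but often misses.

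**The case against.** The strongest case on the other side has four parts.

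*The document is a five-page summary.* Missing-data rules and analysis sets may be in the full plan. This stands. That each test uses only subjects with both values is the default reading of a paired test, not a statement in the text. A reader might infer that the trial has no missing-data rule; the summary cannot show that.

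*The bias is conditional.* Nothing in the documents links leaving to measured volume. Subjects also rate improvement and satisfaction, and dropout driven by those ratings need not follow fringe-projection volume. This stands too. A reader might infer that the late results will be overstated, but the direction could be either way and the bias could be zero.

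*The harm is small in mild cases.* At 10% loss with a weak link the bias is 0.02-0.04 SD, and with skewed data coverage stays near 95%. Low coverage needs normal data, heavy loss and a strong link together. Also, the summary promises tests rather than intervals, and the Wilcoxon test was not simulated, so its behaviour in skewed data is not shown here. The bias in the mean still matters, because the endpoint is a mean change.

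*Visit-wise paired tests are a recognised observed-case analysis, and a long list of added analyses is heavy for secondary endpoints in 55 subjects.* This is fair as to extent. The summary says of touch-up that "A touch-up injection will be made if necessary, according to injector and subject opinion". With a constant touch-up effect, leaving it out of the model cost at most 0.018 SD in the simulated cases, so a touch-up version need not be required. It is not a reason to omit the single model, which needs no new data and loses no precision when dropout is unrelated to response.

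**Conclusion.** The point holds as a worthwhile, low-cost improvement to secondary analyses. On the visible text, the stated method leaves earlier volumes of leavers unused at M9 to M24, and those means are biased if leaving depends on earlier volume change. Under the assumptions above, with normal data, the M24 error is about 0.05-0.14 SD at 20% loss across weak and strong links, and 0.13-0.21 SD at 30% with a strong link. A repeated-measures model brings this close to zero when dropout depends on observed volumes, and only reduces it when dropout depends on unseen ones.

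A reader might go further and conclude that the M6 primary analysis is wrong. The documents do not support that: the modelled loss starts after M6, and the paired test is a valid primary analysis of subjects measured at both visits. Confidence is medium, because every input except the sample size, the visits and the test is assumed.

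**What to change.** Keep the M6 paired test as primary and the visit-wise paired tests as observed-case results. Then add to the SAP:

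- **One likelihood-based repeated-measures model** for mean volume change at M9 to M24 with 95% confidence intervals, in all treated subjects with any post-baseline volume. Include visit and mean-centred baseline volume, with unstructured covariance. Use the same per-subject volume as the primary endpoint, and state how the two areas are combined.
- **A stated fallback** if the model does not converge: compound symmetry with visit-specific variances and robust standard errors, rather than AR(1). In the assumed cases its M24 error is about 0.02 SD or less, against up to about 0.06 for AR(1).
- **The number measured at each visit**, and the M6 change of leavers against stayers, descriptively. Given Step 6, this should not decide whether the model is run.
- **One delta sensitivity analysis** that shifts the predicted missing values from −0.5 to +0.5 SD, since the bias can go either way. At 20% loss the extremes move the mean by 0.20 × 0.5 = 0.10 SD in each direction, and the range covers the 0.15-0.32 SD residual in Step 5.

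A version with touch-up by visit is optional. If the full plan already holds a missing-data rule, refer to it here and reconcile the two.

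Cost: SAP wording, one model, one sensitivity analysis and one table, with no new data or visits. The downside is a little more analysis work, and late results may look less favourable.
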